### ***Pancreatic Amylase Elevation***

Grade 1 ( $> 1.0$  to  $\leq 1.5 \times \text{ULN}$ ) or Grade 2 ( $> 1.5$  to  $\leq 2.0 \times \text{ULN}$ ):

Participants may continue to take the study intervention and should be carefully evaluated and followed closely.

Grade 3 ( $> 2.0$  to  $\leq 5.0 \times \text{ULN}$ ) or Grade 4 ( $> 5.0 \times \text{ULN}$ ):

For asymptomatic Grade 3 pancreatic amylase elevations with no history or concomitant disease of pancreatitis, participants may continue to take the study intervention but should be carefully evaluated and followed closely. For confirmed Grade 4 elevations of pancreatic amylase, participants will have to permanently discontinue the study intervention. If there is clinical

evidence of pancreatitis and amylase of Grade 3 or higher, participants will have to permanently discontinue the study intervention.

### ***Gastrointestinal System***

In case of Grade 4 nausea (hospitalization required) or Grade 4 vomiting (physiologic consequences requiring hospitalization or requiring parenteral nutrition), the participant's continued participation in the study will be at the investigator's discretion.

### ***Musculoskeletal System and Cardiac Muscle***

#### **Myalgia**

Grade 1 (with no limitation of activity):

Participants may continue to take the study intervention and should be carefully evaluated and followed closely.

Grade 2 (muscle tenderness at site other than injection site or with moderate impairment of activity) or Grade 3 (severe muscle tenderness with marked impairment of activity) or Grade 4 (frank myonecrosis):

Participants will have to permanently discontinue the study intervention but can continue in the study. Creatinine phosphokinase should be fractionated for creatine kinase myocardial band (CPK-MB) subunit. Participants having confirmed  $\geq$ Grade 2 myalgia with Grade 3 ( $3.0$  to  $6.0 \times$  ULN) elevation in CPK-MB, or Grade 4 ( $>6.0 \times$  ULN) elevation in CPK-MB subunit will have to permanently discontinue the study intervention.

#### **LDH and LDH-isoenzymes**

For participants with lactate dehydrogenase (LDH) elevation  $>2.5 \times$  ULN, LDH-isoenzymes will be assessed.

#### **Cardiac Rhythm Disturbances**

The following text describes the minimum requirements for the management of cardiac rhythm disturbances; however, additional management decisions are at the investigator's discretion.

Grade 1 (asymptomatic) or Grade 2 (asymptomatic, transient rhythm abnormality not requiring any treatment) cardiac rhythm disturbances:

Participants may continue to take the study intervention and should be carefully evaluated and followed closely.

Grade 3 (recurrent, persistent, symptomatic arrhythmia requiring treatment) or Grade 4 (unstable dysrhythmia requiring hospitalization and treatment) cardiac rhythm disturbances:

Participants will permanently discontinue the study intervention. QTcF prolongation that results in discontinuation of the study intervention will be reported as AE term of "QT prolonged" of

Grade 2 if no symptoms are present. If symptomatic, then a higher grade may be reported as per the definitions above.

### **8.2.7. Other Safety Evaluations**

Visual examination including visual acuity testing, color discrimination, visual field testing, and funduscopy and audiology will be assessed at study site visit indicated in Section 1.3, [Schedule of Activities \(SoA\)](#). The visual examination, audiology test, and funduscopy at Day 1 can be assessed within 4 week prior to Day 1 and within 4 days prior or after each visit other than Day 1.

### **8.3. Adverse Events, Serious Adverse Events, and Other Safety Reporting**

Timely, accurate, and complete reporting and analysis of safety information, including AEs, SAEs, and product quality complaints (PQC) from clinical studies are crucial for the protection of participants, investigators, and the sponsor, and are mandated by regulatory agencies worldwide. The sponsor has established Standard Operating Procedures in conformity with regulatory requirements worldwide to ensure appropriate reporting of safety information; all clinical studies conducted by the sponsor or its affiliates will be conducted in accordance with those procedures.

Adverse events will be reported by the participant (or, when appropriate, by a caregiver or surrogate) for the duration of the study.

Further details on AEs, SAEs, and PQC can be found in Section 10.4, [Appendix 4: Adverse Events, Serious Adverse Events, Product Quality Complaints, and Other Safety Reporting: Definitions and Procedures for Recording, Evaluating, Follow-up, and Reporting](#).

#### **8.3.1. Time Period and Frequency for Collecting Adverse Event and Serious Adverse Event Information**

##### **All Adverse Events**

All AEs and special reporting situations, whether serious or nonserious, will be reported from the time a signed and dated ICF is obtained until completion of the participant's last study-related procedure, which may include contact for follow-up of safety.

##### **Serious Adverse Events**

All SAEs and PQCs occurring during the study must be reported to the appropriate sponsor contact person by study-site personnel within 24 hours of their knowledge of the event.

Serious adverse events, including those spontaneously reported to the investigator within 30 days after the last dose of study intervention, must be reported using the Serious Adverse Event Form. The sponsor will evaluate any safety information that is spontaneously reported by an investigator beyond the time frame specified in the protocol.

Information regarding SAEs will be transmitted to the sponsor using the Serious Adverse Event Form, which must be completed and signed by a physician from the study site and transmitted to the sponsor within 24 hours. The initial and follow-up reports of an SAE should be made by

facsimile (fax). Telephone reporting should be the exception and the reporter should be asked to complete the appropriate form(s) first.

### **8.3.2. Method of Detecting Adverse Events and Serious Adverse Events**

Care will be taken not to introduce bias when detecting AEs or SAEs. Open-ended and nonleading verbal questioning of the participant is the preferred method to inquire about AE occurrence.

### **8.3.3. Follow-up of Adverse Events and Serious Adverse Events**

The investigator is obligated to perform or arrange for the conduct of supplemental measurements and evaluations as medically indicated to elucidate the nature and causality of the AE, or PQC as fully as possible. This may include additional laboratory tests or investigations, histopathologic examinations, or consultation with other health care professionals.

Adverse events, including pregnancy, will be followed by the investigator as specified in Section 10.4, [Appendix 4: Adverse Events, Serious Adverse Events, Product Quality Complaints, and Other Safety Reporting: Definitions and Procedures for Recording, Evaluating, Follow-up, and Reporting](#).

### **8.3.4. Regulatory Reporting Requirements for Serious Adverse Events**

The sponsor assumes responsibility for appropriate reporting of AEs to the regulatory authorities. The sponsor will also report to the investigator (and the head of the investigational institute where required) all suspected unexpected serious adverse reactions (SUSARs). The investigator (or sponsor where required) must report SUSARs to the appropriate Institutional Ethics Committee/Institutional Review Board (IEC/IRB) that approved the protocol unless otherwise required and documented by the IEC/IRB.

### **8.3.5. Pregnancy**

All initial reports of pregnancy in female participants or partners of male participants must be reported to the sponsor by the study-site personnel within 24 hours of their knowledge of the event using the appropriate pregnancy notification form. Abnormal pregnancy outcomes (eg, spontaneous abortion, fetal death, stillbirth, congenital anomalies, ectopic pregnancy) are considered SAEs and must be reported using the Serious Adverse Event Reporting Form. If a participant becomes pregnant during the study, a determination regarding study intervention discontinuation must be made by the investigator in consultation with the sponsor.

Follow-up information regarding the outcome of the pregnancy and any postnatal sequelae in the infant will be required.

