### 5.1. Inclusion Criteria

Each potential participant must satisfy all of the following criteria to be enrolled in the study:

1. Male or female.
2. 20 to 79 years of age, inclusive.
3. Has body weight  $\geq 40$  kg at screening and on Day 1.
4. Has radiological evidence consistent with NTM-LD based on a chest CT scan taken within 6 months prior to screening or at screening.
5. Criterion modified per Amendment 4.
- 5.1 Criterion modified per Amendment 8.
- 5.2 Has at least 2 positive sputum cultures of MAC (sputum cultures to be taken at least 4 weeks apart):

- one obtained within 12 months prior to screening, which was documented while being treated for MAC-LD for a total of at least 6 months.
  - one at screening (by central microbiology laboratory).
6. Criterion modified per Amendment 4.
- 6.1 Criterion modified per Amendment 8.
- 6.2 Received at least 6 months of consecutive MAC-LD treatment (at least 2 antibiotics for MAC, including a macrolide), that is either ongoing or has stopped within 12 months prior to screening.
- Note: Participants must be compliant with medication intake for at least 75% of the total doses for prescribed SOC (including intermittent regimen) recommended by local guidelines. Participants who have missed more than 25% of their doses during a given treatment period for any reason (including noncompliance by participants, interruption due to an AE at the discretion of physician, and others) can only be enrolled if approved by the sponsor's medical monitor.
7. No presence of cognitive dysfunction that would impact the completion of the patient-reported outcome (PRO) assessments.
8. Must sign an informed consent form (ICF) indicating that he or she understands the purpose of, and procedures required for, the study and is willing to participate in the study.
9. A woman of childbearing potential must have a negative highly sensitive serum ( $\beta$ -human chorionic gonadotropin [ $\beta$ -hCG]) test at screening and on Day 1.
10. A woman using oral contraceptives must use an additional contraceptive method (as required in Inclusion Criterion 11).
11. A woman must be (as defined in Section 10.5, [Appendix 5: Contraceptive Guidance](#)).
- a. Not of childbearing potential
  - b. Of childbearing potential and

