## 7. DISCONTINUATION OF STUDY INTERVENTION AND PARTICIPANT DISCONTINUATION/WITHDRAWAL

### 7.1. Discontinuation of Study Intervention

A participant's study intervention must be discontinued if:

- The participant withdraws consent to receive study intervention.
- The investigator believes that for safety reasons or tolerability reasons (eg, AE) it is in the best interest of the participant to discontinue study intervention.

- The participant has a QTcF prolongation (defined as a QTcF value  $\geq 500$  ms, or an increase from baseline of  $>60$  ms) at any given time point (confirmed by repeat ECGs).
- The participant requires treatment with any of the prohibited medications listed in Section 6.8, [Concomitant Therapy](#).
- The participant becomes pregnant. Refer to Section 10.5, [Appendix 5: Contraceptive Guidance](#).
- Noncompliance with study intervention administration as defined in [Table 3](#).
- The participants discontinued administration of study intervention before Week 48 in Group A, Week 60 in Group B or OPW48 in optional cohort.

If a participant discontinues study intervention before Week 48 in Group A, Week 60 in Group B or OPW48 in the optional cohort, the participant will receive the assessments of early discontinuation or withdrawal.

The early discontinuation visit assessment will be performed within 7 days of the investigator's discretion to discontinue treatment with study intervention, unless the participant withdraws consent. Study intervention assigned to the participant who discontinued study intervention may not be assigned to another participant.

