### 9.4.2. Primary Estimand

The primary estimand, the main clinical quantity of interest to be estimated in this study, is defined by the following 5 components:

- Population: Adult patients with treatment-refractory MAC-LD.
- Endpoint: Proportion of participants with sputum culture conversion in MGIT at Week 24.
- Treatment: BDQ-containing regimen versus rifamycin-containing regimen.
- Intercurrent Events (ICE):
  - a. Deaths, treatment discontinuation and treatment regimen changes prior to Week 24: all the ICEs will be handled by a composite strategy to treat the participants as non-convertors.

- b. Major protocol deviations: all data will be used regardless of the occurrence of major protocol deviations (treatment policy strategy).
- Population Level Summary: The difference of proportions between treatment groups.

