## 10.5. Appendix 5: Contraceptive Guidance

Participants must follow contraceptive measures as outlined in Section 5.1, [Inclusion Criteria](#). Pregnancy information will be collected and reported as noted in Section 8.3.5, [Pregnancy](#) and Section 10.4, [Appendix 4: Adverse Events, Serious Adverse Events, Product Quality Complaints, and Other Safety Reporting: Definitions and Procedures for Recording, Evaluating, Follow-up, and Reporting](#).

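### Section 7.1 makes pregnancy an unconditional reason to stop study intervention, but Section 8.3.5 treats stopping as a decision still to be made

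*Protocol*

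**What the plan says.** Three places in the current protocol bear on a participant who becomes pregnant while on treatment.

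- **Section 7.1, Discontinuation of Study Intervention.** The list opens "A participant's study intervention must be discontinued if", and one of its items is "The participant becomes pregnant. Refer to Section 10.5".
- **Section 8.3.5, Pregnancy.** Sites have to notify the sponsor within 24 hours of learning of a pregnancy. For a participant who becomes pregnant during the study, "a determination regarding study intervention discontinuation must be made by the investigator in consultation with the sponsor".
- **Section 10.5, Contraceptive Guidance**, to which Section 7.1 refers. It covers definitions and contraceptive methods, and says "Pregnancy information will be collected and reported as noted in Section 8.3.5".

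The SAP adds nothing on conduct: its Section 5.6.3.4 covers only pregnancy testing and a listing. For the analysis, Section 9.4.2 of the protocol (repeated in SAP Section 5.3.2) groups "Deaths, treatment discontinuation and treatment regimen changes prior to Week 24" as intercurrent events scored as non-conversion.

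**The concern.** Section 7.1 fixes the outcome, while Section 8.3.5 asks someone to decide it. A site that opens one section acts at once; a site that opens the other calls the sponsor and waits for a decision. Both texts are current, and neither defers to the other.

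What is at stake is mainly conduct. Stopping an investigational drug in pregnancy is a safety matter on which sites need one instruction. If treatment continues after a Section 8.3.5 determination, nobody can say from the protocol whether that participant has been handled correctly or has departed from Section 7.1. There is a smaller statistical consequence, because stopping before Week 24 sets the primary endpoint to failure and continuing does not.

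**Working it through.** The plan states no figure on this point, so the check is a comparison of texts, followed by a trace of the analysis consequence.

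**1. Can the event occur?** Yes. Section 5.1 admits women of childbearing potential subject to testing ("A woman of childbearing potential must have a negative highly sensitive serum" test, at screening and on Day 1) and highly effective contraception. A pregnancy on treatment is unlikely but foreseen, which is why Sections 7.1 and 8.3.5 exist.

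**2. Is the Section 7.1 item really unconditional?** The same list shows how it is worded when judgement is intended: one item turns on what the investigator believes to be in the participant's best interest. The pregnancy item has no such wording.

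**3. Does the cross-reference settle it?** No. Section 7.1 leads to Section 10.5, which has no stopping rule and leads on to Section 8.3.5. A site that follows the pointer from the mandatory rule arrives at the text that leaves the matter open.

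**4. Do the two rules collide in every case?**

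| Outcome of the Section 8.3.5 determination | Section 7.1 met? | Section 8.3.5 met? |
|---|---|---|
| Stop study intervention | Yes | Yes |
| Continue study intervention | No | Yes |

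They collide only in the second row. In the first row they still differ on whether there was anything to decide.

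**5. Does anything else depend on Section 7.1?** Section 6.8.2 bars entry to the optional cohort for anyone with a condition described in Section 7.1. The standing of the pregnancy item therefore carries over to that decision.

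**6. Consequence for the primary endpoint.** Under Section 9.4.2, stopping before Week 24 makes the participant a non-converter (composite strategy). If treatment continues and that is later classed as a major protocol deviation, her data are used as observed (treatment policy strategy). The two readings thus fall under different intercurrent-event rules. A different result needs all of the following:

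- the pregnancy is recognised before Week 24. In the Schedule of Activities the tests after Day 1 are at Weeks 12, 24, 36, 48 and 60, so Week 12 is the only scheduled one before Week 24, although Section 8.2.5 allows extra tests at any time;
- the determination is to continue;
- the participant would otherwise have converted.

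With the planned 62 per group, one reclassified participant changes that group's conversion rate by 1/62 = 0.016, or 1.6 percentage points. The sample size in Section 9.2 rests on a difference of 20 percentage points.

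**The case against.** The strongest reply is that the sections are compatible. Section 8.3.5 never tells a site to continue treatment; a site that reports, consults the sponsor and stops has complied with both. Every case reaches the sponsor within 24 hours, so no site has to interpret the wording alone. Section 7.1 is also the dedicated section on discontinuation, whereas Section 8.3.5 sits within safety reporting, so a reader could take Section 7.1 as governing.

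The first two arguments stand and limit the point. A reader might infer that sites hold two opposite orders that cannot both be obeyed; the documents do not support that. The third is a reasonable way to read the protocol, but the protocol states no precedence, and Section 7.1's own pointer leads to Section 8.3.5.

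Two further inferences should be resisted. A reader might add that pregnancy tests 12 weeks apart make the decision come late. The timing of detection is the same whichever section governs, and Section 8.2.5 permits additional tests, so the schedule is a separate matter. A reader might also see a threat to the primary result. The conditions set out above make that at most an isolated case.

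**Conclusion.** The inconsistency is real and is in current text: one section decides the question and another reopens it, with no rule of precedence and a cross-reference that leads back to the open version. It bites only if the determination is to continue, when it is undefined whether continuing is a deviation from Section 7.1.

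The point matters for participant safety and uniform site conduct rather than for inference. The documents give no expected number of pregnancies; that cases will be rare is an assumption based on the contraception requirement and an age range reaching 79 years. On that assumption the effect on the primary analysis is nil or confined to an isolated participant. The correction is still worth making, because sites need a single instruction when a case does arise and the change costs almost nothing.

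**What to change.** Reconcile Sections 7.1 and 8.3.5 so that one instruction governs study intervention when a participant becomes pregnant. State it once and have the other section refer to it. Correct the pointer in Section 7.1 so that it leads to that instruction and not to Section 10.5 alone. Which rule to adopt is for the sponsor and its clinical and safety advisers; no view is offered here.

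In the same text, say whether continuing treatment, if the adopted rule allows it, counts as a protocol deviation. That also settles how the case is handled under Section 9.4.2 and whether it bars entry to the optional cohort under Section 6.8.2.

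The cost is a sentence and a cross-reference at the next amendment, with a short clarification note to sites in the interim. No change to the sample size or the analysis methods is needed.

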### **8.3.6. Disease-related Events and Disease-related Outcomes not Qualifying as Adverse Events or Serious Adverse Events**

All events that meet the definition of an SAE will be reported as SAEs, regardless of whether they are protocol-specific assessments.

### 8.3.7. Adverse Events of Special Interest

The liver, skeletal muscle, heart, pancreas, and stomach have been identified as target organs in nonclinical toxicology studies. Careful monitoring of these organs should be included in clinical studies. Any abnormalities in the parameters related to these target organs are therefore considered as AEs of special interest. Because other compounds for treatment of MAC, with which BDQ will have to be administered, have been associated with rash, skin events are considered as AEs of special interest as well in the study.

## 8.4. Pharmacokinetics

Plasma samples will be used to evaluate the PK of BDQ (and M2 or additional metabolites, if warranted) and CAM (and its active metabolite 4-OH CAM, if warranted). Plasma collected for PK may additionally be used to evaluate safety or efficacy aspects that address concerns arising during or after the study period. Genetic analyses will not be performed on these plasma samples. Participant confidentiality will be maintained.

### 8.4.1. Evaluations

Single sparse blood samples will be collected for measurement of plasma concentrations of BDQ and M2 at Weeks 4, 6, 16, and 32 in Section 1.3, [Schedule of Activities \(SoA\)](#). On Day 1, Weeks 2, 8, 12, 24, and 48, 2 blood samples will also be drawn: the predose and 2 to 4 hours postdose plasma concentrations of BDQ and M2 for Group A, and CAM and 4-OH CAM for both Group A and B. The date and time of the second to last and the last administration of BDQ before the corresponding sample and the date and time of blood draw must be recorded. The date and time of the intake of CAM on the day of sampling and the day before sampling should be recorded. Using these blood samples per participant, the PK exposure of BDQ (if deemed necessary, M2) will be calculated, during the loading phase as well as during the maintenance phase.

Participant confidentiality will be maintained. Additional information about the collection, handling, and shipment of biological samples can be found in the Laboratory Manual.

### 8.4.2. Analytical Procedures

#### Pharmacokinetics

Plasma samples will be analyzed to determine concentrations of BDQ, M2, CAM, and 4-OH CAM using a validated, specific, and sensitive liquid chromatographic-mass spectrometry method by or under the supervision of the sponsor.

If required, some plasma samples may be analyzed to document the presence of circulating metabolites of other analytes (eg, circulating metabolites or denatonium) using a qualified research method. In addition, plasma PK samples may be stored for future analysis of the metabolite profile or concomitant medications.

The bioanalytical report, including a description of the assay and a summary of the assay performance data, will be included in the final clinical study report as an addendum.

